#### **6.1.4 Adjustments for Covariates**

Not applicable to this study.

#### **6.1.5 Handling of Dropouts or Missing Data**

No imputations for missing data will be performed.

#### **6.1.6 Multicenter Studies**

The clinical study will be conducted under a common protocol for each investigational site with the intention of pooling all the data for analysis. Every effort will be made to promote consistency in study execution at each study site.

#### **6.1.7 Examination of Subgroups**

As applicable, data will be summarized in total and by treatment received in ACN03/ACN04.

### **6.2 Disposition of Subjects**

The number of subjects included in the safety population will be summarized for all subjects, for subjects that received Olumacostat Glasaretil Gel, 5.0% in ACN03/ACN04, and for subjects that received Olumacostat Glasaretil Gel, Vehicle in ACN03/ACN04. The number of subjects enrolled, completed, and discontinued (including the reasons for discontinuation) will be summarized similarly.

Subjects who are excluded from the safety population will be summarized by the reasons for exclusion.

### **6.3 Protocol Deviations**

Protocol deviations will not be entered into the database. Deviations will not be programmed or summarized.

### **6.4 Data Sets Analyzed**

#### **6.4.1 Safety Population**

All subjects who receive at least one confirmed dose of Olumacostat Glasaretil Gel, 5.0% and have at least one post-baseline (where baseline is the day that the subject received their first study drug) assessment will be included in the Safety Population. All analyses (efficacy and safety) will be performed using the Safety Population.

### **6.5 Demographic and Other Baseline Characteristics**

All baseline summaries will be done on the safety population.

Sex, race, and ethnicity will be summarized by counts and percentages. Age will be summarized with descriptive statistics.

Age will be carried over from ACN03/ACN04 for those subjects who have the complete date of birth entered into the eCRF.

## **6.6 Prior and Concomitant Medications**

Prior and concomitant medications will be coded to preferred name and anatomical therapeutic chemical (ATC) classification of ingredients using the WHO-DDE.

Counts and percentages will be provided to summarize the use of prior and concomitant medications other than the study drug reported throughout the study. The number and percent of subjects reporting medications will be summarized by ATC level 2 term and preferred name. Ongoing medications and medications ending after the date of first application of Olumacostat Glasaretil Gel, 5.0% (from ACN03/ACN04 or ACN05) will be considered concomitant medications. Incomplete start and end dates which could be prior to first dose or after first dose will be considered prior to first dose.

A by-subject listing of all concomitant medications will be presented.

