## **7 CONCOMITANT MEDICATIONS AND PROCEDURES**

All medications (including over-the-counter drugs, vitamins, antacids and skin care products) taken throughout the study will be recorded on the eCRF.

Medication entries should be specific to the generic name (if a combination drug, then marketed product name) and will include the dose, unit, frequency, route of administration, start date, discontinuation date, and indication. When listing medications indicated for acne, the area treated will be collected.

The Investigator should examine the acceptability of all concomitant procedures, medications, topical preparations and dietary supplements not explicitly prohibited in this study. In order to ensure that appropriate concomitant therapy is administered, subjects will be instructed to consult with the Investigator prior to taking any medication (either self-administered non-prescription drugs or prescription therapy prescribed by another physician).

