## 6.8.2 Adverse Events

AEs from ACN03/ACN04 will be included in the analysis for study ACN05. All AEs will be classified on the basis of Medical Dictionary for Regulatory Activities (MedDRA) terminology. Treatment-emergent AEs (TEAEs) are defined as AEs with an onset on or after the date of the first application of Olumacostat Glasaretil Gel, 5.0% (from ACN03/ACN04 or ACN05). If treatment-emergent status cannot be determined (e.g., unknown date of first application), the AE will be considered treatment-emergent. AEs noted prior to the first study drug administration that worsen after baseline will also be reported as AEs and included in the summaries.

TEAEs will be summarized in total as well as by 12-week periods based on time of onset in relation to date of first application of Olumacostat Glasaretil Gel, 5.0%, based on the definitions below.

- 0-12 Weeks            0 <= onset day <= 85
- >12-24 Weeks        86 <= onset day <= 169
- >24-36 Weeks        170 <= onset day <= 253
- >36 Weeks            onset day >= 254

Summaries will present the number of subjects reporting a TEAE by system organ class (SOC), preferred term, severity, relationship to study drug (causality), and seriousness. When summarizing TEAEs by severity and relationship, each subject will be counted once within a SOC or a preferred term by using the event with the greatest relationship or highest severity within each classification.

All information pertaining to an AE noted during the study will be listed by subject, detailing verbatim term given by the PI or designee, preferred term, SOC), onset date, resolution date, severity, seriousness, action taken, outcome and drug relatedness. The event onset will also be shown relative (in number of days) to date of first application.

Serious AEs (SAEs) will be summarized and listed using the same methodology as noted above. In addition, a listing of subjects who prematurely discontinued from the study due to an AE will be provided.

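### SAP 6.6 classes a stopped medication with an ambiguous incomplete end date as prior, so possible use on the 5.0% gel can only move out of the concomitant counts and listing

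*SAP*

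**What the plan says.** SAP 6.6 defines concomitant use by how a medication ends, not by when it starts. The class is "Ongoing medications and medications ending after the date of first application of Olumacostat Glasaretil Gel, 5.0" per cent, where the first application may come from the parent study (ACN03 or ACN04) or from ACN05. The next sentence deals with partial dates: "Incomplete start and end dates which could be prior to first dose or after first dose will be considered prior to first dose".

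Two outputs follow in the same section. One is a summary: "Counts and percentages will be provided to summarize the use of prior and concomitant medications other than the study drug reported throughout the study". The other is a listing: "A by-subject listing of all concomitant medications will be presented". No listing of prior medications is named there.

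For adverse events, SAP 6.8.2 resolves uncertain timing the other way: "If treatment-emergent status cannot be determined (e.g., unknown date of first application), the AE will be considered treatment-emergent". SAP 6.1.5 says "No imputations for missing data will be performed" and does not mention the medication-date rule. Protocol Section 7 requires that each medication entry "will include the dose, unit, frequency, route of administration, start date, discontinuation date, and indication". Neither that section nor Protocol 11.6 has a partial-date rule.

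**The concern.** In a long-term safety study, uncertain timing is usually resolved towards exposure, so that use which may have overlapped with study drug is shown. SAP 6.6 resolves an uncertain end date away from exposure. Its error has one direction: a medication that was taken on the gel can be labelled prior, but a medication that stopped before the gel is never labelled concomitant.

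The completeness of the concomitant medication output is at stake. That output carries some extra weight because SAP 6.3 keeps protocol deviations out of the database and the summaries, which leaves the medication tables as a main planned place for prohibited acne treatments to show.

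**Working it through.** The plan gives no figure to reproduce. The inputs are the definition and the partial-date rule in SAP 6.6 and the adverse-event default in SAP 6.8.2.

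**Step 1: which records change class.** Let the start date be before first dose, ambiguous, or after it (3 states). Let the end be before, ambiguous, after, or ongoing (4 states). That gives 3 × 4 = 12 combinations. Start after with end before is impossible, so 11 remain. Each cell shows the class under SAP 6.6, then the class if an ambiguous end date were taken as on drug, as 6.8.2 does for events.

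| Start | End before | End ambiguous | End after | Ongoing |
|---|---|---|---|---|
| Before | prior / prior | **prior / concomitant** | concomitant / concomitant | concomitant / concomitant |
| Ambiguous | prior / prior | **prior / concomitant** | concomitant / concomitant | concomitant / concomitant |
| After | impossible | **prior / concomitant** | concomitant / concomitant | concomitant / concomitant |

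The two rules differ in 3 of the 11 cells, all with an ambiguous end date. Down each of the other columns the class is the same whatever the start date, so an ambiguous start date alone changes nothing. In the third differing cell, a known start after first dose means that the end cannot precede first dose. The SAP's own condition, that the date could fall on either side, is then not met. That cell goes wrong only if the end date is read in isolation. Two cells are therefore truly ambiguous.

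**Step 2: how often an ambiguous end date is really after first dose.** The documents give no data on this, so I assume that end dates are uniform over the unknown part, with a 30-day month and a 365-day year. SAP 6.6 requires the end to be after the date of first application, so the inequality is strict.

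- Month known, same month as first dose, first dose on day *d*: share after = (30 − *d*)/30. Day 1: 29/30 = 97%. Day 15: 15/30 = 50%. Day 29: 1/30 = 3%. The mean over days 1 to 30 is 14.5/30 = 48%.
- Year only, same year as first dose, first dose on day *k*: share after = (365 − *k*)/365. Day 1: 364/365 = 99.7%. Day 365: 0%. The mean over the year is 182/365, about 50%.

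At the very last day of the month or year the share is 0, and the rule does no harm.

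**Step 3: where ambiguity can arise.** A month-only end date is ambiguous only in the calendar month of first dose. For subjects who had the 5.0% gel in the parent study, SAP 6.8.1 takes first application from that study, about 12 weeks before ACN05 Day 1, so a month-only end date during ACN05 cannot be ambiguous for them. For former vehicle subjects, first application is in ACN05, so of the 36 weeks only the calendar month containing it is exposed. Their parent-study medications are imported (SAP 6.1), so the cut-point falls inside a period of active recording. Beyond that month, both day and month must be missing.

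**The case against.** The strongest case against is that little turns on this. Start and discontinuation dates are collected, and medications are reviewed at the Week 2 call and at every clinic visit (Protocol 8.2 to 8.5), so badly incomplete dates should be uncommon. The study is descriptive, and no estimate or decision rule uses the classification. SAP 6.6 summarises prior as well as concomitant medications, so a record is relabelled, not discarded. A cautious default for events does not oblige the same default for medications, and the example given in 6.8.2 is an unknown date of first application, not a partial event date. All of this stands and limits the size of the point. It does not supply a reason for the direction chosen in 6.6. The general wording of 6.8.2 still makes the contrast fair as a difference of convention, though not as a contradiction.

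A reader might also infer more than the documents support:

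- *That ambiguous start dates hide drugs begun on treatment.* The definition does not use the start date, and no planned table is said to use it to label a drug as new.
- *That drugs given for on-treatment adverse events are generally undercounted.* Such a drug normally has a known start after first dose, so its end date is not ambiguous.
- *That prohibited acne treatments go unseen.* Step 3 shows how little of ACN05 is reached. There is also another route: need for a prohibited medication is a ground for discontinuation (Protocol 10.2), and reasons for discontinuation are summarised (SAP 6.2).
- *That year-only dates are worse than month-only dates.* Their mean share is about the same, and the share can be lower as well as higher.

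**Conclusion.** The point holds for ambiguous end dates of stopped medications, as a minor improvement. For those records SAP 6.6 always chooses prior, and on average about half would be wrongly placed if end dates are uniform (48% for month-only dates, about 50% for year-only dates). For a given subject the share depends almost entirely on where first dose falls in the month or year. The number of records cannot be computed, because the documents give no rate of incomplete dates. The effect is confined to the descriptive concomitant counts and the by-subject listing; no test, sample size or error rate is touched.

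**What to change.** Replace the partial-date sentence in SAP 6.6 with: *A medication with an incomplete or missing end date will be considered concomitant unless the available start and end date parts show that it ended on or before the date of first application of Olumacostat Glasaretil Gel, 5.0%.* Add a cross-reference to this rule in SAP 6.1.5, so that it is not read as conflicting with the no-imputation statement there.

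This wording changes the class in the three differing cells of the table and leaves the other eight as they are. It also settles the case of a known on-treatment start, and its on-or-before boundary matches the existing definition, which requires an end after first application. The cost is one sentence, one cross-reference and a slight over-count: some medications that stopped before the gel, but whose end date is incomplete, will appear as concomitant.

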## **6.7 Analysis of Efficacy**

### **6.7.1 Primary Efficacy Analysis**

IGA will be summarized with frequency and percent distributions at baseline and final visit (Week 36/ET). The change in IGA level from Baseline to Week 36 will be summarized for the safety population in total, as well as by treatment received in ACN03/ACN04.

A by-subject listing of all IGA results will be presented.

### **6.7.2 Other Supportive Efficacy Analyses**

IGA Scores and Acne Patient Self-Questionnaire assessments will be summarized by visit. Summaries of the frequency and percent distributions of the IGA Scores will be presented and descriptive statistics will be used to summarize the Acne Patient Self-Questionnaire. Satisfaction questions will be summarized with frequency and percent distributions. IGA Scores will be summarized by visit for all subjects as well as by treatment received in ACN03/ACN04.

For subjects receiving Olumacostat Glasaretil Gel, 5.0% in ACN03/ACN04, summary visits will include Baseline and Weeks 12, 24, 36 and 48. For subjects receiving Olumacostat Glasaretil Gel, Vehicle in ACN03/ACN04, summary visits will include Baseline and Weeks 12, 24, and 36.

## 6.8 Safety Evaluation

### 6.8.1 Extent of Exposure

The extent of exposure to study drug in each treatment group will be summarized by total number of days of exposure, total number of applications, number of missed applications, amount of study drug used, amount of study drug per day, percent compliance and number and percentage of subjects who are compliant. A subject will be considered compliant with the dosing regimen if the subject applied 80-120% of the expected number of applications while enrolled in the study.

For subjects receiving Olumacostat Glasaretil Gel, 5.0% in ACN03/ACN04, the date of first application will be from ACN03/ACN04. For subjects receiving Olumacostat Glasaretil Gel, Vehicle in ACN03/ACN04, the date of first application will be from ACN05.

Total number of days of exposure will be computed as follows:

$$\text{Total Exposure} = \text{Date of Last Application} - \text{Date of First Application} + 1.$$

Dosing deviations reported for areas other than the face will not be considered in calculations. On the date of first application and the date of last application, some subjects were to apply one dose and others were to apply two doses, depending on the time of the study visit. After the date of first application and before the date of last application subjects were expected to apply two doses. Missed applications will be calculated from dosing deviations which report zero or one application on a given date. Extra doses will be calculated from dosing deviations which report more than the expected number of applications on a given date.

For subjects receiving Olumacostat Glasaretil Gel, 5.0% in ACN03/ACN04, the total number of applications will be the sum of the applications from ACN03/ACN04 and ACN05, as dosing deviations are specific to the dates of first and last application within each study. The methodology below will be applied to ACN03/ACN04 and ACN05 data separately, then summed.

The total number of applications will be calculated as follows:

If the Date of First Application is not equal to Date of Last Application, then

$$\begin{aligned} \text{Total Applications} &= 2 * (\text{Date of Last Application} - \text{Date of First Application} - 1) \\ &\quad + \text{Expected Applications on Date of First Application} \\ &\quad + \text{Expected Applications on Date of Last Application} \\ &\quad - \text{Missed Applications} + \text{Extra Applications.} \end{aligned}$$

If the Date of First Application = Date of Last Application, then

$$\text{Total Applications} = \text{Expected Applications on Date of First Application} \\ - \text{Missed Applications} + \text{Extra Applications.}$$

Treatment compliance will be based on the expected number of doses given the treatment period duration. Treatment period duration will be computed from the date of first application of Olumacostat Glasaretil Gel, 5.0% (from ACN03/ACN04 or ACN05) and the date of last application.

Then treatment period duration may be calculated as:

$$\text{Treatment Period Duration} = \text{Date of Last Application} - \text{Date of First Application} + 1.$$

Missed applications due to treatment-related AEs will be considered when determining the expected number of doses for each subject. If a treatment-related AE (regardless of location) requires interruption of study drug during the treatment period, missed applications during the AE (onset date to resolution date) will be deducted from the expected number of doses. Therefore, the expected number of applications will be calculated as:

$$\text{Expected Applications} = 2 * (\text{Treatment Period Duration} - 2) \\ + \text{Expected Applications on Date of First Application} \\ + \text{Expected Applications on Date of Last Application} \\ - \text{Applications Missed Due to a Treatment-Related AE.}$$

Percent compliance will be calculated from total number of applications and total number of expected applications as follows:

$$\text{Percent Compliance} = 100 * (\text{Total Applications} / \text{Expected Applications}).$$

Percent compliance will not be calculated for subjects who are lost to follow-up.

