### **6.5 Study Drug Dispensing and Return**

It is the responsibility of the Investigator to ensure that study drug is only used on study subjects enrolled in this study. The study drug must only be dispensed from official study sites by authorized personnel according to the protocol and local regulations.

Study drug will be dispensed by the study site to the subject at each study visit. Two tubes contain enough study drug for 1 month of application. At each visit, the subject will be dispensed enough tubes to allow dosing until the next visit. Partially used tubes may be re-dispensed at the site's discretion.

Subjects are to return all study medication tubes (used and unused) to the study site. Study tubes will be weighed prior to dispensing and upon return, and if required, prior to re-dispensing. Weights will be recorded in the source documents and eCRF.

Each subject is to be instructed on the importance of returning study drug at the next study visit. If a subject does not return study drug, they will be instructed to return it as soon as possible. The site staff will visually inspect the tube to ensure product usage is consistent with the subject's dosing diary.

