### **6.7 Treatment Compliance**

Treatment compliance will be assessed at each visit using a subject-completed diary and visual inspection of the tubes. Subjects will be given a paper diary at each visit in conjunction with study medication. The subject-completed diary will collect application information for the face, chest, back and shoulders. Subjects will be instructed to bring all study medication and diaries to the clinic at the next study visit.

A subject deviating significantly from the assigned dosing regimen on the face, will be counseled. All diaries will be maintained as source documentation.

The first and last dates of study product usage, location and any missed applications will be recorded in the eCRF.

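### SAP 6.8.1 counts days with no dosing information as fully dosed, so application totals and compliance can be overstated by an unknown amount

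*SAP*

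**What the plan says.** SAP 6.8.1 sets the daily starting value: "After the date of first application and before the date of last application subjects were expected to apply two doses". It adds the doses expected on the two end dates, then subtracts missed and adds extra applications. Both corrections depend on a report. For misses, "Missed applications will be calculated from dosing deviations which report zero or one application on a given date". For extras, "Extra doses will be calculated from dosing deviations which report more than the expected number of applications on a given date". Percent compliance is total over expected applications, and 80% to 120% counts as compliant. It is not computed for subjects lost to follow-up. The same section also summarizes the amount of gel used, in total and per day.

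Data capture in Protocol 6.7 fits this design: "The first and last dates of study product usage, location and any missed applications will be recorded in the eCRF". The instrument is a paper diary backed by a look at the tubes: "Treatment compliance will be assessed at each visit using a subject-completed diary and visual inspection of the tubes". Protocol 6.5 adds a site check, "The site staff will visually inspect the tube to ensure product usage is consistent with the" diary, and a weighing step, "Study tubes will be weighed prior to dispensing and upon return".

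On missing data, SAP 6.1.5 says: "No imputations for missing data will be performed". SAP 6.1 and Protocol 11.1 say the same.

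**The concern.** A count by exception is sound only if no report means no miss. With a paper diary, no report can also mean that nobody knows. The formula cannot tell the two apart and resolves both as full dosing. That is an imputation in effect, although the SAP says it makes none.

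Four planned outputs are affected: total applications, missed applications, percent compliance and the percentage compliant. They are meant to show how much drug subjects actually applied over a long course. As defined, a subject with complete diaries and a subject with none can look identical.

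The existing safeguards do not close the gap. The lost-to-follow-up exclusion leaves out subjects who keep attending without a diary, and it is stated for percent compliance only, not for total or missed applications. The visual tube check has no rule that turns a mismatch into a missed dose, and without a diary there is nothing to compare. The amount of gel used is reported beside compliance but not linked to it.

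**Working it through.** The documents state no figure on this point, so there is none to reproduce. The check puts numbers into the SAP's own formulas.

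**Inputs from the documents.** Two applications per day; compliance band 80% to 120% (SAP 6.8.1). Course length is 36 weeks = 252 days for subjects who had vehicle in the parent study, and 12 + 36 = 48 weeks = 336 days for those who had active gel, because their first application date comes from the parent study. Clinic visits are four weeks apart and a diary is issued at each, so one diary covers 28 days = 56 applications.

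**Assumed, because the documents give no rate.** One to three diaries missing per affected subject. The 48-week course is treated as one continuous period.

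**Formulas.** F and L are the first and last dose dates, D = L − F + 1, and e1 and e2 are the doses expected on those dates.

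- Total = 2(L − F − 1) + e1 + e2 − missed + extra
- Expected = 2(D − 2) + e1 + e2 − doses missed for a treatment-related adverse event

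Since D − 2 = L − F − 1, the two are equal whenever no deviation is reported. With two doses on each end date:

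- 252 days: 2 × 250 + 4 = 504 over 504, or 100%
- 336 days: 2 × 334 + 4 = 672 over 672, or 100%

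This result is the same whether the diaries are complete or absent.

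**Case 1: perfect dosing on documented days.** True compliance is (expected − doses not applied) / expected. The SAP scores every row 100%.

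| Course | Diaries missing | True, none of those doses applied | True, half applied |
|---|---|---|---|
| 252 days | 1 | 448/504 = 88.9% | 94.4% |
| 252 days | 2 | 392/504 = 77.8% | 88.9% |
| 252 days | 3 | 336/504 = 66.7% | 83.3% |
| 336 days | 1 | 616/672 = 91.7% | 95.8% |
| 336 days | 2 | 560/672 = 83.3% | 91.7% |
| 336 days | 3 | 504/672 = 75.0% | 87.5% |

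To be wrongly classed as compliant, such a subject must have more than 0.20 × 504 / 2 = 50.4 undosed and undocumented days (252-day course), or 0.20 × 672 / 2 = 67.2 days (336-day course).

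**Case 2: imperfect dosing on documented days.** Let r be the application rate on documented days and f the share of days without information. SAP compliance is 1 − (1 − r)(1 − f). Compliance on documented days is r. With unknown days counted as zero it is r(1 − f). Take r = 0.78 and two diaries missing:

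- 252 days, f = 56/252 = 0.222: SAP 1 − 0.22 × 0.778 = 82.9%; documented 78.0%; unknown as zero 60.7%
- 336 days, f = 56/336 = 0.167: SAP 1 − 0.22 × 0.833 = 81.7%; documented 78.0%; unknown as zero 65.0%

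The SAP score reaches 80% once f = 1 − 0.20/(1 − r). At r = 0.78 that is 0.091, about 23 days of 252 or 31 of 336. At r = 0.70 it is one third, or 84 and 112 days. Subjects just under the threshold are reclassified easily; those well under it are not.

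**The case against.** The strongest objection concerns consequence. A reader might infer that overstated exposure distorts the safety results. The documents do not support that. Days of exposure come from the first and last dose dates, which diary gaps between them do not alter. The target of at least 100 subjects treated for 36 weeks is about duration. Adverse events are summarized as numbers of subjects, in total and by onset period, and no rate per application or per unit of exposure is planned. There is no per-protocol set, so compliance excludes nobody. This stands, and it limits the point to descriptive exposure rows.

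A reader might also infer that compliance is overstated as a matter of fact, and always upward. That goes too far. There is no error if the undocumented doses were applied, or if sites recorded misses from an interview or the tube check, which neither document forbids. Extra doses are also counted only when reported, so an undocumented day can hide those too. Nothing in the documents shows that subjects who do not return diaries dose less.

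Finally, gel use from tube weights is already summarized. It helps, but total weight cannot verify facial dosing in subjects from ACN03 who also treat the trunk, whereas compliance is calculated for the face only.

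None of this removes the defect: the formula gives a definite answer, full dosing, where the data give none.

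**Conclusion.** The point holds in a limited form. Under SAP 6.8.1, days between first and last application with no dosing information default to two applications. This conflicts with the SAP's own no-imputation statement. Total applications can be too high and missed applications too low in any subject. Percent compliance and the percentage compliant can be too high among subjects not lost to follow-up.

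The size is unknown. The worked cases rest on assumed numbers of missing diaries, and the result depends on course length: two wholly undosed diaries put a 36-week subject below 80% but not a 48-week subject, who needs three. A subject with known first and last dates, no diary at all and no other dosing record, and not classed as lost to follow-up, is scored 100% when the truth could lie anywhere from close to 0% up to 100%.

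It is worth correcting because the remedy is cheap and the affected tables otherwise cannot separate documented dosing from absent data. It does not call the planned safety conclusions into question.

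**What to change.** In SAP 6.8.1:

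1. Define a day with neither diary data nor a site-recorded dosing report as unknown, not as dosed.
2. Report the number and percentage of unknown days, in total and by treatment received in the parent study.
3. Keep the present calculation, since Protocol 11.3 defines compliance over the whole time enrolled. Beside it, show compliance over documented days and a sensitivity row that counts unknown days as zero applications.
4. State that the lost-to-follow-up exclusion also covers total and missed applications, or show those subjects separately.
5. Use tube weights only as a descriptive cross-check, and only in subjects who treat the face alone.

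I would not set a minimum diary coverage for calling a subject evaluable. Any cut-off would be arbitrary, and showing the coverage lets the reader judge.

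The cost is a few sentences of SAP text, some programming, and a per-visit field for whether the diary came back if the eCRF lacks one. Reported compliance may come out slightly lower. No clinical procedure changes.
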